3.3 Re-Registration – Inclusion Criteria

3.31 Confirmation that baseline blood sample was drawn and submitted.

3.32 Blood estrogen levels after Cycle 1anastrozole (ANA1) must meet the following criteria:
 $E1 \geq 1.3 \text{ pg/ml}$, AND
 $E2 \geq 0.5 \text{ pg/ml}$

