7.33 Logistics

Study team will contact patients by telephone and tell the patients to either:

1) Continue anastrozole 1mg and go off study.

OR

2) Come to the clinic for an appointment in the next couple weeks (prior to running out of ANA1) to re-register and obtain the new prescription.

Re-registration is required for these patients prior to Cycle 2.

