11.0 Treatment Evaluation/Measurement of Effect

Plasma concentration levels of E1 and E2 will be obtained prior to start of protocol therapy, after 8-10 weeks of anastrozole 1 mg daily (Cycle 1), after 8-10 weeks of anastrozole 10 mg daily (Cycle 2), and after 8-10 weeks of letrozole 2.5 mg daily (Cycle 3).

12.0 Descriptive Factors: None**13.0 Treatment/Follow-up Decision at Evaluation of Patient****13.1 Blood specimens**

- 13.11 Patients for whom the baseline blood sample (prior to treatment on this study) is NOT obtained and submitted, will go off study and be replaced.
- 13.12 Patients for whom the blood sample prior to ANA10 is NOT obtained will go off study and be replaced.

13.2 Anastrozole 1 mg daily for 8-10 weeks (ANA1):

- 13.21 Patients who are able to tolerate anastrozole treatment have no signs of disease recurrence may continue treatment with anastrozole for a maximum of 10 weeks.
- 13.22 Patients who are not able to tolerate anastrozole treatment or develop disease recurrence will discontinue protocol treatment and will go off study where further treatment is at the discretion of her medical team.
- 13.23 Patients who register but then refuse to begin anastrozole treatment will go off study where further treatment is at the discretion of her medical team. Baseline and on study case report forms are to be submitted. On-study material and the End of Active Treatment/Cancel Notification Form must be submitted. No further data submission is necessary.

13.3 At completion of 8-10 weeks of anastrozole 1 mg daily for 8-10 weeks

- 13.31 Patients who have completed a minimum of 8 weeks and maximum of 10 weeks of anastrozole 1 mg daily and whose plasma concentrations of E1 and E2 meet one of the following criteria:

- (a) $E1 > 1.3 \text{ pg/ml}$ and $E2 \leq 0.5 \text{ pg/ml}$
- (b) $E1 \leq 1.3 \text{ pg/ml}$ and $E2 > 0.5 \text{ pg/ml}$
- (c) $E1 \leq 1.3 \text{ pg/ml}$ and $E2 \leq 0.5 \text{ pg/ml}$

will go off study where further treatment is at the discretion of her medical team.

- 13.32 Patients who have completed a minimum of 8 weeks and maximum of 10 weeks of anastrozole 1 mg daily and whose plasma concentrations of E1 and E2 are such that:

$E1 \geq 1.3 \text{ pg/ml}$ and $E2 \geq 0.5 \text{ pg/ml}$

may re-register and begin treatment with anastrozole 10 mg daily for 8-10 weeks. Patients who choose not to re-register will go off study where further treatment is at the discretion of her medical team.

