16.0 Statistical Considerations and Methodology

16.1 Study Design

This goal of this study is to assess whether women with inadequate estrogen suppression after 8-10 weeks of adjuvant anastrozole 1 mg daily (ANA1) would benefit from increasing their dose of anastrozole to 10 mg daily (ANA10). Two analytic approaches will be taken to address this objective. The first approach focuses on the set of patients who are adherent to treatment schedule, that is, if at least 80% of the planned dose is taken will adequate estrogen suppression be achieved. The second approach focuses on intentions, that is, among those patients who start an 8-10 week course of anastrozole 10 mg daily what proportion will have achieved adequate estrogen suppression at treatment discontinuation. Patients who fail to provide a blood sample after discontinuing treatment will be considered not to have achieved adequate estrogen suppression.

The study was designed to assess in the adherent cohort whether the estrogen suppression rate with anastrozole 10 mg daily for 8-10 weeks (ES-ANA10) after inadequate estrogen suppression of 8-10 weeks of adjuvant anastrozole 1 mg daily is at most 25% against the alternative that it is at least 50%.

Inadequate estrogen suppression is defined as $E1 > 1.3 \text{ pg/ml}$ and $E2 > 0.5 \text{ pg/ml}$ after 8-10 weeks of treatment with an aromatase inhibitor.

Based on preliminary findings from MA27, we expect approximately 20% of women with ER+ primary breast cancer to have inadequate estrogen suppression with anastrozole 1 mg daily for 8-10 weeks. Thus, if 160 patients were enrolled then we would expect 32 of them to have IES-ANA1. There may be a few patients who refuse to switch to anastrozole 10 mg daily for 8-10 weeks followed by a blood draw for E1 and E2 testing.

Assuming at most 3 women will refuse to continue or fail to adhere to treatment, 29 patients who are adherent to treatment will be available to evaluate the primary aim.

With a sample size of 29 patients in the adherence cohort, a one-sided binomial test of proportions with a significance level of 0.05 will have a 87% chance of rejecting the null hypothesis that the estrogen suppression rate with anastrozole 10 mg daily for 8-10 weeks is at most 25% when the true estrogen suppression rate with anastrozole 10 mg daily for 8-10 weeks is at least 50%. Specifically, the null hypothesis is rejected if the number of women who are ES-ANA10 is 12 or more among these 29 patients.

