16.2 Analyses

16.2.1 Primary Analysis

The primary analysis will include all patients with inadequate estrogen suppression after 8-10 weeks of adjuvant anastrozole 1 mg daily who provide a blood sample after completing 8-10 weeks of anastrozole 10 mg daily will be included in the analysis of the primary endpoint. Patients who fail to provide a blood sample after discontinuing anastrozole 10 mg daily for 8-10 weeks

Adverse events will be graded and their attributions assigned using NCI CTCAE v5.0.

For each cohort, point and interval estimates for the estrogen suppression rate with anastrozole 10 mg daily for 8-10 weeks will be constructed using the properties of the binomial distribution.

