16.4 Stopping rules

16.41 Feasibility stopping rule

The percentage of patients who have inadequate estrogen suppression ($E1 > 1.3 \text{ pg/ml}$ and $E2 > 0.5 \text{ pg/ml}$) will be examined after every 25th patients has completed 8-10 weeks of anastrozole at the 1 mg daily dose. If this percentage is 10% or less among these 25 patients and all the previously enrolled patients is 10% or less, the trial will temporarily halt for the study team to review study data to make a trial recommendation to FDA and IRB.

16.42 Safety Stopping rule:

Adverse events will be examined at the completion of each treatment. Enrollment to the trial will be temporarily halted if:

- (a) During or at completion of treatment Cycle 1 with anastrozole 1 mg daily, 2 or more of the first 6 patients or 30% or more of the patients treated with the agent have developed a Grade 4 cytopenia or some other Grade 3-4 adverse event during or at completion of that agent
- (b) During or at completion of treatment Cycle 2 with anastrozole 10 mg daily, if 2 or more of the first 6 patients develops a DLT (as specified in Section 7.0 of the protocol) within 28-35 days of starting ANA10. The study will remain closed to enrollment to allow the study team to review toxicity data thoroughly and make decisions regarding changes to the protocol. If at most one of these 6 patients develops a DLT within 28-35 days of starting ANA10, re-registration will reopen.

After at least 7 patients have been re-registered and have begun ANA10, 30% or more of the patients treated with the agent have developed a Grade 4 cytopenia or some other Grade 3-4 adverse event during or at completion of that agent

- (c) During or at completion of treatment Cycle 3 with letrozole 2.5 mg daily, 2 or more of the first 6 patients or 30% or more of the patients treated with the agent have developed a Grade 4 cytopenia or some other Grade 3-4 adverse event during or at completion of that agent
- (d) A patient death on protocol treatment or within 30 days of discontinuing all protocol treatment that is considered possibly, probably or definitely related to treatment.

The study team will review study data and then make a trial recommendation to FDA and IRB.

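### Inadequate suppression is defined with > in 16.1 and 16.41 but with ≥ for entry to 10 mg and in the cut-point derivation, so on-threshold values are classified inconsistently

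*Combined protocol and SAP*

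**What the plan says.** **Entry to 10 mg is inclusive.** Section 3.32 requires "E1 \geq 1.3 \text{ pg/ml}$, AND" the matching condition E2 ≥ 0.5. Sections 7.32 and 13.32 give the same rule. Section 7.33 adds that "Re-registration is required for these patients prior to Cycle 2", so 3.32 has to be met before 10 mg is given.

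**The source of the cut points is inclusive.** In 1.1 the indicator equals 1 for a value at or above the candidate cut point. In 1.2 the 2.2-fold risk overall, and the 3.0-fold risk on anastrozole, belong to women at or above both thresholds.

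**The statistical section is strict.** Section 16.1 states: "Inadequate estrogen suppression is defined as $E1 > 1.3 \text{ pg/ml}$ and $E2 > 0.5 \text{ pg/ml". The feasibility rule in 16.41 uses the same operators: "The percentage of patients who have inadequate estrogen suppression ($E1 > 1.3 \text{ pg/ml}$ and $E2 > 0.5 \text{ pg/ml". Section 1.4 speaks of levels above the thresholds.

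**Section 13.31 is the complement of the strict rule.** Its off-study list begins with "a) $E1 > 1.3 \text{ pg/ml}$ and $E2 \leq 0.5 \text{ pg/ml", so it takes in women whom 13.32 allows to re-register.

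**The primary set depends on the defined term.** Under 16.2.1, "The primary analysis will include all patients with inadequate estrogen suppression after 8-10 weeks of adjuvant anastrozole 1 mg daily" and who give a blood sample after 10 mg. Adequate suppression has no definition of its own.

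**The concern.** One phrase, inadequate suppression, determines who is in the primary analysis, what counts as success and when the feasibility rule fires. In 16.1 and 16.41 it carries a different boundary from the rule that selects women for ten times the standard dose, and from the boundary to which the risk evidence applies.

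Three consequences follow if the text is taken literally and adequate is read as the complement of 16.1:

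- **Population.** A woman with one hormone exactly on its threshold and the other at or above its own can be given 10 mg under 3.32, yet she does not have inadequate suppression for 16.2.1.
- **Outcome.** A woman whose E2 falls from 0.6 to 0.5 with E1 still at or above 1.3 is scored as adequately suppressed. The same values would have qualified her for escalation, and they lie in the raised-risk group of 1.2.
- **Feasibility.** Section 16.41 counts a narrower group than the one that can re-register.

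The decision rule is a fixed count: "the null hypothesis is rejected if the number of women who are ES-ANA10 is 12 or more among these 29 patients". A single reclassified woman can therefore decide the result, and the boundary should be settled before data are seen.

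**Working it through.** **1. Reproduce the design.** Inputs from 16.1: null rate 0.25, alternative 0.50, n = 29, reject at 12 or more, one-sided 0.05.

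- Yield: 160 × 0.20 = 32; 32 − 3 = 29.
- Size: P(X ≥ 12 | 29, 0.25) = 0.0390.
- Power: P(X ≥ 12 | 29, 0.50) = 0.8675, which matches the stated 87%.

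The design figures are correct.

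**2. Put values on and around the thresholds through each rule.**

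| E1, E2 (pg/ml) | 3.32, 7.32, 13.32 | 13.31 | 16.1 |
|---|---|---|---|
| 1.4, 0.6 | qualifies for 10 mg | not listed | inadequate |
| 1.3, 0.6 | qualifies for 10 mg | off study | not inadequate |
| 1.4, 0.5 | qualifies for 10 mg | off study | not inadequate |
| 1.3, 0.5 | qualifies for 10 mg | off study | not inadequate |
| 1.4, 0.4 | does not qualify | off study | not inadequate |
| 1.2, 0.6 | does not qualify | off study | not inadequate |

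The rules disagree on the three middle rows, where at least one value is exactly on its threshold and neither is below. Off the thresholds they agree.

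**3. How much could it matter?** The documents give neither the share of women on a threshold nor the decimal precision of reported results, so no overall figure can be derived. The following is an illustration only. It needs an analyst to mix the definitions: ≥ to select the 29, > to score the outcome.

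Assumptions: one of the 29 enters with E2 on 0.50 and E1 at or above 1.3; the other 28 convert at the null rate of 25%; she truly converts with chance 0.25; otherwise her level is unchanged and she is wrongly scored a success if E2 repeats exactly, with chance r. Her success chance is then 0.25 + 0.75r.

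- If she is a sure failure: P(X ≥ 12 | 28, 0.25) = 0.0294. If a sure success: P(X ≥ 11 | 28, 0.25) = 0.0679. Difference 0.0385.
- Size = 0.0294 + 0.0385 × (0.25 + 0.75r). With r = 0 this returns 0.0390.
- For r: the inter-assay CV for E2 at 0.50 is 8.5% (14.41), so the SD of one reading is 0.085 × 0.50 = 0.0425, and of the difference of two readings 0.0425 × √2 = 0.0601. A repeat means a change within half a reporting unit.

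| Assumed precision | SD used | r | 0.25 + 0.75r | Size |
|---|---|---|---|---|
| 0.01 pg/ml | 0.0601 | 0.066 | 0.300 | 0.041 |
| 0.01 pg/ml | 0.0425 | 0.094 | 0.321 | 0.042 |
| 0.1 pg/ml | 0.0601 | 0.595 | 0.696 | 0.056 |
| 0.1 pg/ml | 0.0425 | 0.761 | 0.821 | 0.061 |

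Variation within a woman beyond assay error would lower r and these sizes. If one definition is used for both entry and outcome, no woman starts as a success and size stays at 0.039.

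**The case against.** The strongest reply is that this touches only exact ties, that their number is unknown, and that any single definition applied throughout keeps the test valid. All of that stands. Under a consistently strict reading the 25% null refers to the strict endpoint and size remains 0.039. The illustration above arises only from a mixture that the plan does not instruct.

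Three stronger readings are tempting, and the documents do not support them.

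- **Lost power.** A reader might infer that on-threshold women are subtracted from the 29 and that power falls. Section 16.1 defines inadequate suppression strictly and then counts 32 such women, less 3. Read literally, the 32 and 29 are already the strict group, and on-threshold women come on top of them. Section 16.3 also gives 160 as a minimum.
- **Two cohorts that disagree.** A reader might infer that the second approach must include an on-threshold woman whom the primary set omits, because it asks "among those patients who start an 8-10 week course of anastrozole 10 mg daily what proportion will have achieved adequate estrogen suppression". That is one reading. Section 16.1 offers both approaches for the same objective, which concerns women with inadequate suppression on 1 mg, so both cohorts may be subsets of the strict group. The second cohort has no stated test.
- **13.31 as a lone slip.** It conflicts with 13.32, 3.32 and 7.32, but it agrees with 16.1, 16.41 and 1.4. If sites followed 13.31, on-threshold women would never take 10 mg and the population problem would vanish. The outcome problem would remain.

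None of this reconciles the rules. Two boundaries run through the protocol and no section says which governs.

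**Conclusion.** The inconsistency is real and should be fixed. Sections 3.32, 7.32 and 13.32 share the boundary of the risk evidence in 1.1 and 1.2; 16.1, 16.41, 13.31 and 1.4 do not. Followed as written, a value that qualifies a woman for escalation is not inadequate in the primary analysis, and the same value after 10 mg counts as adequate. The second statement rests on reading adequate as the complement of 16.1, since no other definition is given.

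The size of the effect is unknown and may be small. In the mixed-definition illustration, one on-threshold woman takes the size from 0.039 to 0.041–0.042 if results are reported to 0.01 pg/ml, and to 0.056–0.061 if reported to 0.1 pg/ml; both precisions are assumptions. The sample size, cut-off, size and power in 16.1 are sound. The fault lies in the definition of the population and endpoint.

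**What to change.** - In 16.1 and 16.41, define inadequate suppression as E1 ≥ 1.3 and E2 ≥ 0.5 pg/ml, and state that adequate suppression is E1 < 1.3 or E2 < 0.5.
- In 16.2.1, say that the population uses this definition.
- Rewrite 13.31 as the exact complement of 13.32: (a) E1 ≥ 1.3 and E2 < 0.5; (b) E1 < 1.3 and E2 ≥ 0.5; (c) E1 < 1.3 and E2 < 0.5.
- In 1.4, change above to at or above.
- It would also help to state the decimal precision at which results are compared with the thresholds.

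The cost is wording in five sections. No patients, samples or data are added, and n = 29, cut-off 12, size 0.039 and power 0.868 stay as they are. The change does not deal with chance readings just below a threshold, which occur under either definition.

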16.2 Analyses

16.2.1 Primary Analysis

The primary analysis will include all patients with inadequate estrogen suppression after 8-10 weeks of adjuvant anastrozole 1 mg daily who provide a blood sample after completing 8-10 weeks of anastrozole 10 mg daily will be included in the analysis of the primary endpoint. Patients who fail to provide a blood sample after discontinuing anastrozole 10 mg daily for 8-10 weeks

Adverse events will be graded and their attributions assigned using NCI CTCAE v5.0.

For each cohort, point and interval estimates for the estrogen suppression rate with anastrozole 10 mg daily for 8-10 weeks will be constructed using the properties of the binomial distribution.

16.3 Accrual rate and enrollment

Accrual Rate: MCR – anticipate 300 patients per year meeting eligibility criteria and 100 patients per year agreeing to participate in the clinical trial.

Total Expected Accrual: 160 minimum to obtain 32 patients who reach Cycle 3 with 29 patients evaluable for study endpoints

16.4 Stopping rules

16.41 Feasibility stopping rule

The percentage of patients who have inadequate estrogen suppression ($E1 > 1.3 \text{ pg/ml}$ and $E2 > 0.5 \text{ pg/ml}$) will be examined after every 25th patients has completed 8-10 weeks of anastrozole at the 1 mg daily dose. If this percentage is 10% or less among these 25 patients and all the previously enrolled patients is 10% or less, the trial will temporarily halt for the study team to review study data to make a trial recommendation to FDA and IRB.

16.42 Safety Stopping rule:

Adverse events will be examined at the completion of each treatment. Enrollment to the trial will be temporarily halted if:

- (a) During or at completion of treatment Cycle 1 with anastrozole 1 mg daily, 2 or more of the first 6 patients or 30% or more of the patients treated with the agent have developed a Grade 4 cytopenia or some other Grade 3-4 adverse event during or at completion of that agent
- (b) During or at completion of treatment Cycle 2 with anastrozole 10 mg daily, if 2 or more of the first 6 patients develops a DLT (as specified in Section 7.0 of the protocol) within 28-35 days of starting ANA10. The study will remain closed to enrollment to allow the study team to review toxicity data thoroughly and make decisions regarding changes to the protocol. If at most one of these 6 patients develops a DLT within 28-35 days of starting ANA10, re-registration will reopen.

After at least 7 patients have been re-registered and have begun ANA10, 30% or more of the patients treated with the agent have developed a Grade 4 cytopenia or some other Grade 3-4 adverse event during or at completion of that agent

- (c) During or at completion of treatment Cycle 3 with letrozole 2.5 mg daily, 2 or more of the first 6 patients or 30% or more of the patients treated with the agent have developed a Grade 4 cytopenia or some other Grade 3-4 adverse event during or at completion of that agent
- (d) A patient death on protocol treatment or within 30 days of discontinuing all protocol treatment that is considered possibly, probably or definitely related to treatment.

The study team will review study data and then make a trial recommendation to FDA and IRB.

16.5 Analysis Plan for Secondary Outcome and Translational Endpoint

Descriptive statistics will be used to describe the distribution of E1 and E2 concentrations following ANA10 and letrozole. The percent change in E1 and E2 concentrations from pre-AI levels will be determined and graphically depicted using spider plots.

16.6 Data & Safety Monitoring

16.61 Safety review

The principal investigator(s) and the study statistician will review the study monthly to identify accrual, adverse event, and any endpoint problems that might be developing.

The Mayo Clinic Cancer Center (MCCC) Data Safety Monitoring Board (DSMB) is responsible for reviewing accrual and safety data for this trial at least biannually, based on reports provided by the MCCC Statistical Office.

16.7 Subset Analyses for Minorities

16.71 Study availability

This study will be available to all eligible female patients, regardless of race or ethnic origin.

16.72 Statistical analysis by subset

There is no information currently available regarding differential effects of this regimen in subsets defined by race, gender, or ethnicity, and there is no reason to expect such differences to exist. Therefore, although the planned analyses will look for differences in treatment effect based on racial groupings, the sample size is not increased in order to provide additional power for subset analyses.

16.73 Regional population

The geographical region served by MCCC has a population which includes approximately 3% minorities. Expected sizes of racial by gender subsets are shown in the following table:

Ethnic Category	Accrual Targets		
	Females	Males	Total
Hispanic or Latino	5		5
Not Hispanic or Latino	155		155
Ethnic Category: Total of all subjects	160	0	160
Racial Category			
American Indian or Alaskan Native			
Asian	7		7
Black or African American	6		6
Native Hawaiian or other Pacific Islander			
White	147		147
Racial Category: Total of all subjects	160	0	160

Ethnic Categories:

Hispanic or Latino – a person of Cuban, Mexican, Puerto Rican, South or Central American, or other Spanish culture or origin, regardless of race. The term “Spanish origin” can also be used in addition to “Hispanic or Latino.”

Not Hispanic or Latino**Racial Categories:**

American Indian or Alaskan Native – a person having origins in any of the original peoples of North, Central, or South America, and who maintains tribal affiliations or community attachment.

Asian – a person having origins in any of the original peoples of the Far East, Southeast Asia, or the Indian subcontinent including, for example, Cambodia, China, India, Japan, Korea, Malaysia, Pakistan, the Philippine Islands, Thailand, and Vietnam. (Note: Individuals from the Philippine Islands have been recorded as Pacific Islanders in previous data collection strategies.)

Black or African American – a person having origins in any of the black racial groups of Africa. Terms such as “Haitian” or “Negro” can be used in addition to “Black or African American.”

Native Hawaiian or other Pacific Islander – a person having origins in any of the original peoples of Hawaii, Guam, Samoa, or other Pacific Islands.

White – a person having origins in any of the original peoples of Europe, the Middle East, or North Africa.

